#### Village-level experiment (Research Questions 1, 2 and 3)

#### *Study Design*

We will start by identifying 700 markets, along with the most centrally located village and the mosque attended by most residents of that village. We expect this to comprise about 250 households, or 500 adults per village. We will call this entity a “market+” (plural: markets+).

In order to evaluate whether masks prevent the spread of COVID by preventing transmission and/or protecting the wearer, we will randomize markets+ into treatment and control groups. Our intervention will involve distributing masks at no cost at mosques, markets and directly at people’s homes. We will combine the mask distribution with appropriate behavior change communication and messaging involving imams, market committee leadership and community leaders. We will stratify on markets+ within the same upazila, keeping all markets+ at least 5-10 km apart to minimize spillovers.

Half of the 700 markets+ will be assigned to the treatment group. We intend to stratify to that treatment and control groups are as balanced as possible in terms of ex ante likelihood of COVID-19 infections. To do so, we will: 1) stratify by upazilas and 2) stratify by unions that have similar case rates. For “markets+” that are in the same Upazila and in unions with similar rates of cases, we will list them in order of population and do pairwise stratification by population.

[figure not shown]

Figure 1: Village-level experiment study design

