  - We will encourage local community leaders to endorse a statement mandating that everyone wear masks
  - Community mask promoters will go door to door to each household in the market+ and distribute up to 2 masks to each household (one for each household member) and discuss the value of wearing masks in public. During these household visits our surveyors will wear masks and maintain physical distance whenever possible; they will also cleanse their hands with hand sanitizer between each household visit. This will occur immediately after our baseline survey.
- At mosques:
  - Distribute one mask to each worshipper as he enters the mosque for Jummah prayer each Friday.
  - Provide imams with behavior change communication to encourage regular and appropriate mask use in public areas, both in the mosque and elsewhere. Imams will variously appeal to men as guardians of their family's health, men as individuals who want to stay healthy so they can continue working, as respected business owners and leaders in the community, and as business owners who want to continue to keep their businesses open. They will also reinforce that men should share the messages about the importance of wearing masks with their families in order to help keep them safe.
  - Hand out a visual brochure produced by the World Health Organization (WHO) that underscores the value of mask wearing and shows how to properly wear and clean a mask.
- At markets:
  - Speak to the committee of shop owners at each treated market, explain the importance of mask use, and ask them to commit to wearing masks, as well as directing the market vendors to wear a mask at all times.
  - Every other day, distribute one mask to each person who visits the markets and hire one mask promoter to encourage all people at the market to wear masks by emphasizing the individual's duty and ability to keep their community safe
  - Have an agreement with the officials managing the market to also encourage people to wear masks on days when our monitors are not present
  - Hand out the aforementioned brochure on the masks
  - An audio recording reminding people to please wear masks will play at markets periodically

Control groups will not be included in mask distribution or mask promotion. We will distribute masks that are manufactured specifically for this project and have a distinctive color and design, so that our enumerators can directly observe whether people are wearing the distributed masks or other masks.

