#### Symptoms of respiratory symptoms

- Go to each household and conduct in-person our baseline survey (same questions as telephone survey). We will elicit consent, as well as collecting demographic information such as age, gender, employment status, and household size information.
- Conduct two waves of follow-up phone surveys to elicit respiratory symptoms and ask about mask use: we will conduct these five weeks after the start of the intervention, and nine weeks after the start, with the potential for longer-term follow-up surveys. We will determine the response rate in the pilot, but our initial estimate is at least 70%.
- Monitor differences in response rates between the treatment and control group to assess whether there is possible response bias from people in the treatment group being more likely to complete our full telephone survey (we suggest other ways of mitigating this potential bias below). For 5,000 randomly chosen households, we will draw blood spots from one adult identified as the highest-risk in their household in terms of number of contacts (2,500 in the control group and 2,500 in the treatment group); the blood spots will be collected in the baseline household survey and used for serology tests. This will allow us to see if survey response rates to our telephone survey correlate differently with baseline infectivity in the treatment and control group.
- Recruit and train local pharmacists to collect data on the number, fraction, and gender of customers that report various symptoms of respiratory infection. Pharmacists will also record the count and purpose of the medicines purchase to treat fever, dry cough or sore throat, and the number of family members with each symptom.

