#### Assessing SARS-CoV-2 infection Via Serologic Testing

In both the market+ and individual-level experiment, we are interested in assessing the impacts of mask use on COVID-19 infections separately from respiratory disease. To do so, we will use serological testing.

In the market+ experiment, serological tests will be conducted 12 weeks after baseline for individuals who reported respiratory disease symptoms during our intervention. We will follow-up with these individuals using household interviews and conduct serology tests using blood spots obtained from finger pricks. The number of positive serology tests in this population will tell us rates of “symptomatic COVID-19”. We will then compare rates of symptomatic COVID-19 between the treatment and control group. For example, if 5% of the 350,000 respondents in the market+ experiment report respiratory symptoms, we will conduct 17,500 such tests. Symptomatic COVID-19 will be a subset of cases of respiratory disease. Power will be similar to our respiratory disease calculation above, especially if most respiratory disease cases are COVID-19. If infection rates are higher than expected, we will cap the number of serology tests at 20,000, which should be sufficient to have ample power based on the calculation above. In addition, we will conduct baseline and endline serologic testing in a random selection of 5,000 households. This is to evaluate factors that could be related to differential reporting between the control and treatment groups.

Dried blood spot samples will be collected at endline from individuals who reported COVID-like symptoms as well as from the 5,000 randomly-selected individuals at baseline and endline. Rapid diagnostic tests will also be performed at endline. Only samples that are positive by rapid diagnostic test and 5% of negative samples will undergo further evaluation by ELISA.

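### Door-to-door mask distribution follows at once on the baseline survey that enrols households, in treatment villages only, so enrolment can depend on the arm and no safeguard is stated at that stage

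*Protocol*

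**What the plan says.** **Allocation.** Under Study Design (Section IV, item 3), the protocol states that "we will randomize markets+ into treatment and control groups" and that "Half of the 700 markets+ will be assigned to the treatment group". Stratification uses upazila and union case rates, and within those strata "we will list them in order of population and do pairwise stratification by population". No household data enter the allocation.

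**Enrolment.** Under Data collection, for both arms, staff are to "Go to each household and conduct in-person our baseline survey". Consent and demographic details are taken at that visit. Section V, item 5, gives the task of presenting the consent form to the implementing partner.

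**Masks, treatment arm only.** Under Intervention activities, "Community mask promoters will go door to door to each household in the market"+, and of this step: "This will occur immediately after our baseline survey". The sentence on infection precautions at the same visits says: "During these household visits our surveyors will wear masks and maintain physical distance whenever possible". Control villages get neither masks nor promotion.

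**Calendar.** Section I, item 1, gives September 23rd both for the start of the initial survey (called a phone survey there) and for the start of mask distribution and promotion.

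**Safeguards stated.** Response to the telephone surveys is to be monitored by arm. Blood spots are taken in 5,000 random households, 2,500 per arm, at the baseline household survey.

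**The concern.** When clusters are randomised first and individuals are enrolled afterwards, randomisation protects the individual comparison only if enrolment does not depend on the arm. Here the step that could make it depend on the arm, a free good brought to the door, is placed directly after the enrolment visit and in one arm only. Staff who know the arm may persist more or less at the door. In a village of about 250 households, those visited later may already know that masks are on offer.

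The enrolled set matters for the outcomes. The symptom outcome covers people whose phone numbers were collected. Only adults who report symptoms by telephone are tested for the primary outcome. If enrolment differs by arm in number or kind, the primary comparison mixes that difference with the mask effect, and a larger sample does not dilute it.

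The protocol recognises the same mechanism one stage later, where it expects that treated people may be more willing to complete the telephone survey. It does not apply that reasoning to the baseline visit.

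**Working it through.** **1. The plan's own figures.** 500 people × 700 markets+ = 350,000 respondents per wave; 0.05 × 350,000 = 17,500 tests. Both reproduce. Half of 350,000 is 175,000 per arm.

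**2. Is the arm known at enrolment?** This is an inference from four places.
- Allocation needs only area and population data, so it can precede household contact (Study Design).
- Baseline blood spots are planned as 2,500 per arm, so allocation appears to exist by then (Data collection).
- Masks follow the survey at once in one arm, and both activities start on the same date (Intervention activities; Section I, item 1).
- The partner that takes consent also hands out masks (Section V, items 1 and 5). Asked how participants are identified and contacted, the protocol answers for villages with the mask visits themselves.

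No concealment of the arm from baseline staff is stated, nor a roster fixed before allocation is disclosed, nor a comparison of enrolment by arm.

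**3. Reach of the stated safeguards.** Telephone response is conditional on enrolment. The blood spots are too, since they are taken at the same visit. They cover one adult per household: 5,000 / 350,000 = 1.4% of expected respondents.

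**4. Illustration with no true mask effect.** Let enrolment be e₁ (treatment) and e₀ (control), and let the extra people enrolled under treatment have r times the risk of the others. Then the rate ratio is [e₀ + (e₁ − e₀) × r] / e₁. The values of e₁, e₀ and r are assumptions; the protocol gives none.

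| e₁ vs e₀ | r | Calculation | Rate ratio |
|---|---|---|---|
| 95% vs 90% | 0.5 | (0.90 + 0.025) / 0.95 | 0.974 |
| 92% vs 90% | 0.5 | (0.90 + 0.010) / 0.92 | 0.989 |
| 95% vs 90% | 1.5 | (0.90 + 0.075) / 0.95 | 1.026 |
| 92% vs 90% | 1.5 | (0.90 + 0.030) / 0.92 | 1.011 |

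The last two rows apply if households with more illness are the ones drawn in by masks; the bias then hides a benefit.

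**5. Scale against what the trial could detect.** Detectable relative reduction = (1.96 + 0.84) × √[2p(1 − p)/n_eff] / p, with n_eff = 175,000 / (1 + 499 × ICC). Two-sided 5%, 80% power and the ICC are assumed; p = 5% is the protocol's example symptom rate, and p = 1% is an assumed rate for a rarer outcome.

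| ICC | p = 5% | p = 1% |
|---|---|---|
| 0 | 4.1% | 9.4% |
| 0.005 | 7.7% | 17.6% |
| 0.01 | 10.1% | 23.1% |
| 0.02 | 13.7% | 31.2% |

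A shift of 2.6% is between 2.6/4.1 = 63% and 2.6/13.7 = 19% of the detectable reduction in symptoms, and a smaller share for a rarer outcome. A shift of 1.1% is between 27% and 8%.

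**The case against.** The case on the other side is substantial.

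- **Who hands out masks.** A reader might infer that the surveyors who enrol households also bring the masks. The protocol does not support that as fact: it names community mask promoters, and surveyors appear only in the precaution sentence. One organisation doing both jobs does not show that the same individuals do. The text is unclear, and the point does not need them to be the same people.
- **Order.** Masks come after the survey, so each household's consent precedes its own masks. The baseline survey might also mean the whole village wave, in which case part of the remedy is already planned. The wording allows this, but it does not say that the village baseline closes first, and the common start date does not help.
- **No choice of whom to approach.** Every household is visited in both arms, which removes selective approach. Contact, refusal and willingness to give a phone number can still vary by arm.
- **Later repair.** A reader might infer that an imbalance could never be seen or corrected. That goes too far. Demographics are collected from those surveyed, village population is known, and blood spots allow baseline seroprevalence to be compared by arm. These checks are partial, because each of the individual-level ones sees only people who enrolled.
- **Size.** A reader might take the ratio of people enrolled, 0.95/0.90 = 1.056, as a 5.6% bias in the primary result. That would apply to raw counts at equal risk. The serology section does say "The number of positive serology tests in this population will tell us rates", but it goes on to compare rates, so the 1.1% to 2.6% shifts above are the relevant ones.

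**Conclusion.** The point stands as a weakness in the stated field sequence. It does not show that bias will occur. Following the protocol as written, enrolment takes place when staff probably know the arm and free masks are arriving in one arm only, and the stated checks begin after enrolment. That staff know the arm is a strong inference and is not stated.

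The size cannot be derived from the document. On assumed enrolment gaps of 2 to 5 percentage points and extra people at half or one and a half times the usual risk, the rate ratio without any mask effect lies between 0.974 and 1.026. That is smaller than the detectable effect in every setting tabulated, so it would be unlikely to create a finding alone. It could still add noticeably to, or subtract from, a modest one. An analysis plan cannot fully repair this afterwards, because the households that did not enrol leave no outcome data.

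**What to change.** 1. In each matched pair, complete the household roster, consent, baseline survey and baseline blood spots in both villages before allocation is disclosed to the baseline survey staff and before any mask promotion begins.
2. Access permissions from imams, market managers and community leaders (Section IV, item 6) may be obtained earlier, in the same wording in both arms and without disclosing allocation.
3. Reword the household step under Intervention activities so that the planned promoters start only once the village baseline is closed, and state whether surveyors take part in those visits.
4. Use the locked roster of listed adults as the denominator, and report households approached and enrolled by arm. The roster does not replace concealment: with 95% against 90% enrolled and r = 0.5, cases found per listed adult would still differ by (0.90 + 0.025)/0.90 = 1.028.

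**Cost.** A short delay in treatment villages. If promoters already call separately, little else changes. If survey and hand-out were to share a visit, a separate call is needed, at most about 350 × 250 = 87,500 households. No extra participants or tests are required.

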### *Data collection*

We will conduct the following activities in both control and treatment arms.

#### Appropriate mask use

- Count the number of mosque-goers (every Friday), market-goers (one day per week), and people in public near the village entrance, indoor restaurants as people enter or exit who are a) appropriately (covering the nose and chin) wearing a mask distributed by our project, b) appropriately wearing a mask that was not distributed by our project, c) inappropriately wearing any a mask or other face covering, or d) are not wearing a face covering at all, and also the fraction specifically wearing our distinctive mask.

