throughout Bangladesh, compliance was high, with 80-95% of respondents reporting that they wore masks in public areas.

Our more recent data, as well as our conversations with officials, suggests that this trend has now reversed. The Bangladeshi government formally mandated mask use in late May and began fining non-compliers; nonetheless, in our latest survey of mask use, we observed 100,000 people in public areas throughout Bangladesh and found that only 26% were wearing masks despite the severity of the epidemic continuing to increase.

3. **Research Plan:** Summarize the study design and research procedures using non-technical language that can be readily understood by someone outside the discipline. If working with a Non-Government Organization (NGO) or other organization, be sure to highlight which are research-only activities and which activities would occur regardless of the research. If working with survey firms, please specify what research activities the research firm will be responsible for.

We have four main research questions we seek to answer:

1. Can mask distribution and promotion at mosques, markets, and homes successfully change community mask-wearing norms from the status quo to appropriate wearing of high-quality masks?
2. Can community mask-wearing reduce the transmission of symptomatic respiratory infections and symptomatic COVID-19 infection?
3. Does mask-wearing induce risk-compensation such as an increase in leaving the home or reduced physical distancing?
4. Can mask-wearing reduce the risk of COVID-19 infection for the individual mask wearer?

To answer the first three questions, we will randomize an intervention package at the level of markets and associated villages.

To answer the fourth question, we will randomly choose a small fraction of high-risk individuals in control regions and provide them masks and instructions for proper mask use to assess whether masks protect against infection.

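### During distribution, every Friday mosque count and about half of possible market count days coincide with treatment-arm mask hand-outs, so these counts can overstate the norm change in Research Question 1

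*Protocol*

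**What the plan says.** All references are to the protocol.

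- **Counting.** Section IV.3, Village-level experiment, Data collection, Appropriate mask use: "Count the number of mosque-goers (every Friday), market-goers (one day per week), and people in public near the village entrance". The market day is not specified. The section introduces its procedures with "We will conduct the following activities in both control and treatment arms".
- **Mosque hand-out, treatment arm.** Intervention activities: "Distribute one mask to each worshipper as he enters the mosque for Jummah prayer each Friday".
- **Market hand-out, treatment arm.** Intervention activities: "Every other day, distribute one mask to each person who visits the markets and hire one mask promoter to encourage all people at the market". Market officials also agree to "encourage people to wear masks on days when our monitors are not present", so market days without project staff are foreseen.
- **Control arm.** "Control groups will not be included in mask distribution or mask promotion".
- **Use of the counts.** They supply secondary outcome 1, mask use at mosques, markets and other public places. Research Question 1 asks whether the package can "successfully change community mask-wearing norms from the status quo to appropriate wearing of high-quality masks".
- **Duration.** Section I, item 1 has distribution, promotion and field observation all running through the 12 weeks from 23 September to 12 December. The Intervention activities text in Section IV.3 limits the activities to four weeks.

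**The concern.** The mosque count and the mosque hand-out share a place and a day in every week of distribution. The market count can fall on a hand-out day, and no rule prevents it. Both happen in the treatment arm only, so randomisation does not remove the difference.

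The observation categories do not separate the two either. They distinguish a project mask from another mask, and correct from incorrect wearing. They do not distinguish a mask accepted at the door from one brought from home. A worshipper who puts the mask on at the entrance and takes it off on the way home could be recorded as a success.

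Wearing a mask at the point of distribution, under staff prompting, is weak evidence of a changed community norm or of the consistent use named in Aim 1. If Research Question 1 is answered from these counts, delivery of masks may be read as a change in habit, and the package recommended elsewhere on that basis. The rule governs data collection, so a statistical analysis plan cannot fully repair it: if no mosque-goer is classified before the hand-out, no clean mosque figure exists for the distribution period.

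**Working it through.** The protocol gives no target or power figure for mask use, so there is no stated number to reproduce. Two checks apply.

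**1. How often counts and hand-outs coincide**

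Inputs: study period 23 September to 12 December 2020 (Section I); Friday mosque counts and one market count per week (Appropriate mask use); Friday and every-second-day hand-outs (Intervention activities). The period has 81 days and 12 Fridays, 4 of them in the first 28 days.

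| Reading of duration | Friday mosque counts on a hand-out | Market days that are hand-out days |
|---|---|---|
| Distribution throughout (Section I) | 12 of 12 | 40-41 of 81 (49-51%) |
| Four weeks (Section IV.3), within those weeks | 4 of 4 | 14 of 28 (50%) |
| Four weeks, counts continuing to the end | 4 of 12 (33%) | 14 of 81 (17%) |

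A fixed market weekday does not avoid the overlap. Over 28 days, an every-second-day schedule hits any given weekday in half of the weeks.

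**2. What the overlap could do to the figure**

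Spurious rise = s × h × (1 − p), where

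- s is the share of counts that follow a hand-out: 1 at mosques and 0.5 at markets while distribution runs, taking the worst case that the count comes after the hand-out;
- p is use with no norm change, set to 0.26. This is the observed share in public areas across Bangladesh (Section IV.2, Current Situation), not a mosque or market baseline;
- h is the share of non-wearers who put a mask on only because it was just handed to them. The documents give no value; the range 10-50% is an assumption.

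During distribution:

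- Mosques, h = 10%: 1 × 0.10 × 0.74 = 7.4 points. h = 50%: 1 × 0.50 × 0.74 = 37 points.
- Markets, h = 10%: 0.5 × 0.10 × 0.74 = 3.7 points. h = 50%: 0.5 × 0.50 × 0.74 = 18.5 points.

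If distribution lasts 4 of 12 weeks and all weeks are averaged, each figure is multiplied by 4/12:

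- Mosques: about 2.5 to 12.3 points.
- Markets: about 1.2 to 6.2 points.

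If the count is taken before the hand-out or away from it, s = 0 and the spurious rise is 0.

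**The case against.** The strongest reply has five parts.

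- **The order is not stated.** A reader might infer that the protocol counts people after they receive a mask. It does not say so. The wording about entering or leaving follows the mention of restaurants and may not apply to mosques, and classifying worshippers as they arrive is compatible with the text. This stands: the defect is an unspecified order, not a stated post-hand-out count.
- **Clean counts exist.** Village-entrance and restaurant counts have no stated hand-out at the same spot, although Section V, Recruitment Procedures, adds hand-outs at tea stalls and factories. On the four-week reading, later counts are free of hand-outs everywhere. This also stands, but the protocol does not say that Research Question 1 rests on those counts.
- **Masks come from elsewhere too.** Households receive up to two masks door to door, so some worshippers will arrive already wearing one. True. This shrinks the pool of non-wearers, and with it the bias, but a count after the hand-out could not show it.
- **Wearing at a hand-out is real wearing.** A reader might infer that inflated uptake makes the infection effect look too small per unit of mask use. The documents do not support that. A mask worn at prayer or in the market is real exposure, and a market day chosen without regard to the schedule represents average market use during distribution. Using only staff-free days for that purpose would understate it.
- **Reporting by venue and period may sit in an analysis plan that is not shown.** That is fair for the analysis. It does not settle where and when the observer counts.

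**Conclusion.** The point holds in a limited form. While distribution runs, all Friday mosque counts and about half of possible market count days coincide with a treatment-only hand-out, and nothing separates the two. Used as evidence for Research Question 1, these counts can overstate the norm change.

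The direction of the possible bias is clear; its size is not. The ranges of about 7-37 points at mosques and 4-19 at markets rest on the assumed h, the national 26% figure, no norm change, and counts taken after the hand-out. They are illustrations, not estimates.

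A reader might go further and conclude that the trial's main result is compromised. It is not: mask use is a secondary outcome, and the primary serology outcome is not biased by how masks are counted. This should be fixed before counting begins, but it is not a must-fix.

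**What to change.** In Section IV.3, Appropriate mask use:

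1. Classify mosque-goers on approach, before they reach the hand-out point.
2. Record for each market count whether it is a hand-out day, and schedule the weekly count so that staff-free days are covered. Use the same weekday and time in the paired control village.
3. State that the norm claim under Research Question 1 rests on counts made before or away from hand-outs, including village-entrance, restaurant and post-distribution counts.
4. Report hand-out-day counts separately, and keep them when describing average mask use for interpreting the infection result.

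Section I and the Intervention activities text must also be reconciled on how long distribution runs, because this decides how many counts overlap.

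The cost is some rescheduling of counters and moving the mosque observation point. The protocol does not give the counters' rota, so whether extra visits are needed cannot be judged from it. The reported uptake is likely to be less favourable.
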